In this study we are recruiting women who have had preeclampsia in the past 5 years. We use the blood vessels in the skin as a representative vascular bed. Using a minimally invasive technique (intradermal microdialysis for the local delivery of pharmaceutical agents) we examine the blood vessels in a nuckle-sized area of the skin in women who have had preeclampsia. We make these measurements after the subjects take a placebo and after they take losartan (an angiotensin II receptor blocker) to test whether this treatment improves vascular function in these women. Because losartan can have dangerous effects on a fetus, women enrolled in this study will be required to use an effective form of birth control [hormonal patch, implant or pill; intrauterine device; consistent use of barrier contraceptive; or prior medical procedure to prevent pregnancy (i.e. tubal ligation or vasectomy in current partner)]. As a compliment to these measurements, we also draw blood from the subjects and isolate the inflammatory cells to test how sensitive their inflammatory responses are following the placebo and the losartan treatment.

A modification was submitted changing the eligibility requirements from having preeclampsia within the past 2 years, to within the past 5 years. This modification was made to help with recruitment for the study. Women who are breastfeeding are excluded from this study. Since many women are breastfeeding during those first 2 years after delivery, it reduced those that were eligible for the study. We changed it to delivering within the past 5 years to match the other preeclampsia studies in our lab (IRB #202203433, 202303202, 202303799).

I.5

Specify your research question(s), study aims or hypotheses (do not indicate "see protocol")

AIM: To determine the effect of systemic AT1R inhibition (oral losartan) on in vivo and in vitro measures of inflammation and endothelial function in women who have had preeclampsia (PE) . Utilizing a chronic (6 week) losartan intervention coupled with intradermal microdialysis and assessment of the inflammatory response to ang II stimulation in peripheral blood mononuclear cells (PBMC), we will test the hypotheses that therapeutic doses of the AT1R inhibitor augment endothelium-dependent dilation and reduce inflammation in PE.

HYPOTHESES

- 1: Chronic oral losartan therapy will augment endothelium-dependent dilation in PE by increasing nitric oxide-dependent dilation.

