- 2: Chronic oral losartan therapy will attenuate exaggerated ang II sensitivity in PE.
- 3: Chronic oral losartan therapy will reduce circulating inflammatory cytokines, and attenuate the exaggerated inflammatory response to ang II stimulation in PBMCs from PE.

NOTE: This IRB protocol encompasses the projects of aim 3 in the attached NIH K99/R00 award. Aim 2 has been completed and aim 1 is approved under HawkIRB #201909818.

I.6

**Background and significance and/or Preliminary studies related to this project.
(do not indicate "see protocol")**

Angiotensin II Sensitivity Contributes to Endothelial Dysfunction Following Preeclampsia: Women with a history of preeclampsia have an exaggerated pressor response to systemic infusion of Ang II. Similarly, compelling *in vivo* pilot data from our lab demonstrates that this increased sensitivity to Ang II is present in the microcirculation and contributes to endothelial dysfunction postpartum in formerly preeclamptic patients. Ang II mediates several events of the inflammatory process including activation of the vascular endothelium; and AT1R activation plays a large role in the pathophysiology of concurrent inflammatory reactions through this direct action on local vascular cells. Inhibition of Ang II, either through ACE inhibition or AT1-receptor antagonism, reduces tissue inflammation and oxidative injury. Reciprocally, inhibition of inflammatory mediators such as IL-17 producing T cells blunts the pressor response to systemic Ang II infusion in animal models of hypertension. Collectively, increased sensitivity to Ang II coupled with the role of Ang II signaling in chronic inflammation, suggests that these factors are likely reciprocal, and contribute to microvascular dysfunction and elevated CVD risk in women who have had preeclampsia.

AT1 Receptor Inhibition Is a Viable Intervention Strategy to Mitigate CVD Risk Following Preeclampsia: The clinical symptoms of preeclampsia (high blood pressure, proteinuria, edema, etc.) typically resolve within 12 weeks post-partum. However, despite this absence of

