- *Use 3rd person active voice "The Principal Investigator will identify subjects. For example, the principal investigator will identify potential subjects, the study coordinator will discuss the study with subjects over the telephone and schedule the first study visit, etc..."*
- *Describe the steps that will be taken by the research team to minimize the possibility of coercion or undue influence during the consent process*

The subjects will consist of healthy women (age 18 and older) who have delivered a baby within the past 5 years and had preeclampsia during their pregnancy, but were free of cardiovascular or metabolic disease prior to pregnancy. These subjects will be enrolled and complete losartan and placebo treatments in a double-blind randomized crossover design. The PI and research staff will recruit subjects from Johnson county and surrounding areas via advertisements, flyers, emails, The UI mass-email system, newspaper and newswire ads, Research Match.org, obtaining contact information from the Maternal Fetal Tissue Bank (MFTB) registry, utilizing TriNetX (discussed in more depth below), and posting on the UIHC website for research volunteers. Recruitment materials (attached MFTB recruitment letter) will be sent to women registered with the MFTB who fit our inclusion criteria and have consented to be contacted for future studies. The UIHC Clinical Trials and Research Website will have this research study available as a listed research study for potential research subjects to find out more information and express interest in participating. Additionally, paid advertisements (see attached IC Mom Ad) will be posted on the Iowa City Moms website and social medias. These advertisements when clicked will link to the study's page on the UIHC Clinical Trials and Research website.

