VII.E.2 *Describe randomization scheme/assignment including ratio such as 1:1, 2:1 etc.*
Subjects will be randomized to which treatment they receive first (placebo or losartan). All subjects will complete both arms of the study. They will be blinded to which treatment they are receiving at the time of the treatments. If they wish to know, subjects can be informed which treatment they received at what time when they complete the study.

VII.E.3 *Will any questionnaires, surveys, or written assessments be used to obtain data directly from subjects in this study?*
Yes

VII.E.4 *List all questionnaires, surveys, written assessments and ATTACH each one to the application. (NOTE: You are NOT prohibited from attaching copyrighted materials to this application)*
pre-consent screening survey
additional information survey
health history questionnaire

VII.E.5 *Does this project involve creating any audiotapes, videotapes, or photographs?*
No

VII.E.6 *Provide a detailed description in sequential order of the study procedures following the consent process - DO NOT cut and paste from the Consent Document.*

Describe study populations separately if they will be participating in different procedures - include CONTROL population if applicable.

DESCRIBE:

- *What subjects will be asked to do/what happens in the study (in sequential order)*
- *The time period over which procedures will occur*
- *The time commitment for the subject for individual visits/procedures*
- *Long-term followup and how it occurs*

Visit 1 - Consent and Screening (approximately 1 hour)

The PI or research staff explain the study and go over the informed consent with the participant. After the participant signs the informed consent, the PI or research staff performs the physical screening that includes urine pregnancy test, heart rate (HR), blood pressure (BP), height, waist circumference, and weight measurements. The participant fills out the health history questionnaire and confirms that they are using an effective form of birth control. A research nurse performs or approved laboratory personnel standard venipuncture to obtain blood (total = 7.5ml blood) for complete blood count (CBC), chemistry analysis, and lipid profile to be measured at UIHC pathology labs. The subject provides a urine sample for the measurement of urine proteins which will be measured by the UI Diagnostic Lab.

Visits 2 and 5- Pick up study medications (approximately 15 minutes)

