The PI or research staff give the participant study medication (losartan or placebo). The PI or research staff goes over the instructions for taking the study medication which includes how many pills to take and at what times of day, potential side effects, and who to call if they have questions or problems while taking the medication.

Visits 3 and 6 - Pick up 24 hour blood pressure monitor (approximately 15 minutes)

The PI or research staff instrument the participant with the 24 hour blood pressure monitor. The PI or research staff goes over the instructions for wearing the monitor.

Visits 4 and 7 - Experimental visits (approximately 4 hours each)

Note: prior to coming to PSRB for the experimental visits, subjects take the oral study medication for 6 weeks. Subjects will ingest 1 pill per day. After the first study visit, subjects will undergo a washout period of at least 14 days in which they do not ingest any study medication, before beginning the same 6 week regimen of the other treatment.

In the event of an experimental failure (e.g. equipment stops working, building power outage during study visit, etc) subjects may be asked to repeat a trial.

Experimental procedures

24 hours before the study visit, subject will be instrumented with a 24 hour blood pressure monitor to wear home for 24 hours. Subject will return the blood pressure monitor to the investigators when they come in for the experimental visit.

Subjects will come to the CRU or 118 PSRB where a research nurse or approved laboratory personnel performs a blood draw (14.5 ml, < 1 Tablespoon) for substances of interest (e.g. inflammatory cytokines) and immune cell activity, and blood chemistry. The subject provides a urine sample for the measurement of urine proteins which will be measured by the UI Diagnostic Lab. Then the rest of the study visit occurs in 118 PSRB for the experiment (Pulse wave velocity and intradermal microdialysis).

Pulse wave velocities (PWV) on Carotid-femoral and carotid-brachial: Carotid-femoral artery PWV, the 'gold standard' in vivo assessment of aortic

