The -80C freezer in 111 PSRB is a shared wet lab space. The door to this lab space is kept locked but those with keys to the shared lab space would be able to enter the room. Individuals with key access to 111 PSRB include:

[name]
[name], BS
[name], BA

X.7***Does your study meet the NIH criteria for a [Certificate of Confidentiality](#) or will you be applying for Certificate of Confidentiality?***

Yes

X.8***If yes, provide rationale:***

Per Section 2012 of the 21st Century Cures Act as implemented in the 2017 NIH Certificates of Confidentiality Policy, all ongoing or new research funded by NIH as of December 13, 2016 that is collecting or using identifiable, sensitive information is automatically issued a CoC.

XI. Data Analysis**XI.1*****Describe the analysis methods you will use, including, if applicable, the variables you will analyze***

The primary outcome variable will be cutaneous vascular conductance, which is calculated from laser-Doppler flux/mean arterial pressure. Three-way repeated measures ANOVA (treatment, MD site, dose) will be used to examine systemic treatment differences (losartan vs. placebo) and local

microdialysis treatment differences across the doses of pharmacological stimuli. Appropriate post-hoc analyses with corrections for multiple comparisons will be performed when main effects are identified, including potential confounding variables as covariates. Paired t-tests will be used to examine systemic treatment differences on pulse wave velocity.

XI.2***Provide the rationale or power analysis to support the number of subjects proposed to complete this study.***

Based on previous data examining chronic pharmacological intervention strategies we calculate that 10 subjects will be necessary to detect an effect size of 15% between microdialysis sites (1 sample RMANOVA, power=0.08, $\alpha=0.05$). Based on the duration of the intervention and prior experience, we anticipate that ~5 subjects will screen but not be eligible and of those that enroll, ~5 will drop out of the intervention, therefore, we suggest a total sample of 20 subjects.

XII. Future Research**XII.1*****Do you wish to keep any information about subjects involved with this research project so that members of the current research team may contact them in the future for your own research projects?***

Yes

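### The two-period crossover is analysed without a period term, so the losartan main effect depends on the completer split if outcomes change between visits

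*Combined protocol and SAP*

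**What the plan says.** Section VII.D.29 describes the design: "These subjects will be enrolled and complete losartan and placebo treatments in a double-blind randomized crossover design". Section VII.E.2 adds: "Subjects will be randomized to which treatment they receive first (placebo or losartan". The form asks there for the allocation ratio; the answer gives no ratio, block size or balance rule. Under VII.E.6 each treatment lasts 6 weeks, and between treatments "subjects will undergo a washout period of at least 14 days in which they do not ingest any study medication". The two experimental visits are therefore at least 8 weeks apart (2 + 6).

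Section XI.1 makes CVC the primary outcome and analyses it by "Three-way repeated measures ANOVA (treatment, MD site, dose"; those three are the only factors named. For the other outcome, "Paired t-tests will be used to examine systemic treatment differences on pulse wave velocity". Covariates appear once, in the sentence on post-hoc comparisons: "including potential confounding variables as covariates". No variable is named there.

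Two hypotheses in I.5 bear on the point. The first is "Chronic oral losartan therapy will augment endothelium-dependent dilation in PE by increasing nitric oxide-dependent dilation" and the second is "Chronic oral losartan therapy will attenuate exaggerated ang II sensitivity in PE".

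**The concern.** In a two-period crossover, each woman's losartan-minus-placebo difference carries any change between her two visits. The sign depends on which treatment came first. If equal numbers complete each order, these contributions cancel from the mean but stay in the variance. If the numbers differ, part of the change remains in the estimate, and the planned output cannot separate it from losartan.

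Equal numbers are not assured. No balance rule is stated, and XI.2 expects about 5 enrolled women to drop out.

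The exposure is limited to the treatment main effect:

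- **Exposed:** pulse wave velocity, and the part of hypothesis 1 that says losartan augments endothelium-dependent dilation.
- **Depends on the test chosen:** hypothesis 2 is exposed if tested as the losartan main effect at the single angiotensin II probe, but not if tested as treatment-by-dose.
- **Spared under an additive shift:** the nitric-oxide contrast in hypothesis 1, which is treatment-by-site.

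**Working it through.** **Inputs from the documents (XI.2).** 10 completers, alpha 0.05, a 15% effect between microdialysis sites, power printed as 0.08, about 5 screen failures and about 5 dropouts.

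**Assumptions.** The printed power means 0.80; tests are two-sided; the 15% is borrowed as a 15-point losartan effect; π (period 2 minus period 1) runs from 0 to 15.

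**The plan's own figures.** The total reproduces: 10 + 5 + 5 = 20. The 10 does not, because no SD or within-woman correlation is given. Solving backwards from the noncentral t (n = 10, effect 15, power 0.80) gives an SD of the difference of 15.06. Hence π = 3 is about 0.2 SD and π = 7.5 about 0.5 SD.

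**Shift.** Let τ be the losartan effect, n1 the placebo-first and n2 the losartan-first completers. The expected difference is τ + π in placebo-first women and τ − π in losartan-first women. The unadjusted mean therefore has expectation τ + π(n1 − n2)/(n1 + n2). The shift is 0 at 5:5, 0.2π at 6:4 and 0.4π at 7:3, with the sign reversed at 4:6 and 3:7. The ANOVA treatment F equals the squared paired t on per-woman means (5.2306 both ways in one simulated data set), so the result covers both CVC and pulse wave velocity.

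**Chance of imbalance among 10 completers.**

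| Allocation assumed | Unequal | 7:3 or worse |
|---|---|---|
| Simple randomisation | 75% | 34% |
| 15 start 8:7, 5 drop out at random | 61% | 12% |

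**Equal split.** At 5:5, π adds about π² × n/(n − 1) to the estimated variance. For π = 7.5 that is 56.25 × 10/9 = 62.5 on top of 15.06² = 226.8, so the apparent SD rises to √289.3 = 17.0. Simulated power, planned versus period-adjusted:

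| π | Planned | Adjusted |
|---|---|---|
| 0 | 80% | 79% |
| 3 | 79% | 79% |
| 7.5 | 72% | 79% |
| 15 | 48% | 79% |

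With other SDs, at π = 7.5: 87% versus 93% (SD 12) and 50% versus 55% (SD 20).

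**Unequal split, π = 7.5, true effect 15.** At 6:4 the planned estimate is 15 ± 0.2 × 7.5, that is 16.5 or 13.5, with power 80% or 62%; adjusted power is 77%. At 7:3 it is 15 ± 0.4 × 7.5, that is 18 or 12, with power 88% or 53%; adjusted power is 72%. The adjusted estimate stays at 15.

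**Type I error of the planned test.** Averaged over simple randomisation it is 5.0%, 5.0% and 5.2% at π = 3, 7.5 and 15. For a given split at π = 7.5 it is 3.0% (5:5), 3.7% (6:4) and 6.0% (7:3).

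**Average power, planned versus adjusted.**

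| π | Simple randomisation | 8:7 start |
|---|---|---|
| 0 | 80% vs 74% | 80% vs 77% |
| 3 | 78% vs 74% | 80% vs 77% |
| 7.5 | 71% vs 74% | 74% vs 77% |
| 15 | 50% vs 74% | 55% vs 77% |

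The curves cross near π = 6, and 6/15.06 is about 0.4 SD.

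**Mean squared error.** With v = (1/n1 + 1/n2)/4, the planned estimate is the better one when π is below SD × √(v − 0.1)/(|n1 − n2|/10). This gives 4.9 at 6:4 and 5.2 at 7:3, about a third of the SD.

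**The case against.** The strongest answer is that randomising the order already protects the comparison. That stands on average: under simple randomisation the planned tests are unbiased and keep their level. A reader might infer that the missing term makes the tests invalid or the losartan estimate biased by design. The documents do not support that. Nothing in them shows that a period effect exists, and the procedures described are the same at both experimental visits. The shift arises only given an unequal split, can go either way, and vanishes at 5:5.

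Second, adjustment is not free. For a period effect below about 0.4 SD it loses power on average, and the large gains need a period effect as big as the assumed drug effect. This stands, and makes the adjustment insurance rather than a repair.

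Third, the power figures borrow a between-site effect for a between-treatment comparison and rest on a back-solved SD. This also stands. Only the omission and the shift formula are certain.

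Fourth, the covariate phrase might admit treatment order. It belongs to the post-hoc sentence and names no variable, so it does not put period into the main test or into a paired t-test.

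A reader might also infer that order should be crossed with the whole ANOVA. That would move the treatment-by-site test to n − 2 df and unweighted sequence means. An 80% power there would fall to 79%, 77% and 72% at 5:5, 6:4 and 7:3, with no gain under an additive shift.

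**Conclusion.** The concern holds, conditional on the split obtained and for the treatment main effect only. XI.1 omits period from the analysis of a crossover whose sequence balance is not assured. The consequence is a shift of 0.2π at 6:4 or 0.4π at 7:3, or some lost power at 5:5 if π is sizeable. The formula needs no assumed SD. The power figures do: they rest on SD 15.06, a 15-point effect, and reading 0.08 as 0.80. The imbalance probabilities rest on the two allocation models shown. The real size of harm is unknown because the documents give no period effect and no SD. The sparing of the interactions assumes an additive shift; a proportional change in flux between visits would not cancel. The change is worth making because it uses data already held, but its absence does not invalidate the trial.

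**What to change.** If the treatment codes have not been analysed, state in XI.1 that two comparisons use the period-adjusted crossover t-test: the average of the two sequence means, with pooled within-sequence variance and n − 2 df. They are the losartan-versus-placebo main effect on CVC (per-woman mean over doses, overall or at the relevant site) and pulse wave velocity. Keep the planned ANOVA for treatment-by-site and treatment-by-dose, and do not cross order with those terms.

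If the codes have been analysed, keep the planned tests as primary and report the period-adjusted results as a labelled sensitivity analysis. This may well apply: VII.B.1.c puts the last visit at 08/31/2024, and the title page shows a download date of 6/2/2025. Report the completer split by sequence in either case.

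No new data are needed, since order is fixed by the randomisation. With no period effect, main-effect power falls from 80% to 79% at 5:5 (the lost degree of freedom), 77% at 6:4 and 72% at 7:3 (at 7:3 mostly the unequal weighting). On average the adjustment gains power only when π exceeds about 0.4 SD. It does not address carryover.

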Microdialysis Probe Insertion: (NOTE: The intradermal microdialysis procedure used here is identical to the one approved in IRB #201909818) Please see the attached "intradermal microdialysis" document for general information about intradermal microdialysis, schematic representation of the procedure, and references. The researchers place a tight band around the forearm so they can visualize veins. For each MD site, they make pairs of pen-marks on the arm 2.5 cm (1 inch) apart and away from veins. They remove the tight band. The MD tubing enters and exits the skin at the marks. The researchers clean the arm with povidone iodine and alcohol, and place an ice bag on the site for 5 minutes to numb the skin. Then they insert a thin needle into the skin at each entry mark. The needle's tip travels between the layers of skin for 2.5 cm (1 inch) and exits the skin at the matching exit-mark. They thread the microdialysis tubing through the needle and then withdraw the needle leaving the tubing in the skin. Any hyperemia related to the insertion subsides in about 60 minutes. When the hyperemia induced by inserting the tubing in the skin subsides, the experiment begins. During this time Lactated Ringer's perfuses the tubing. The researchers tape a fiber optic laser Doppler flowmeter probe and its holder over each microdialysis site. The researchers control the temperature of the holders. The holders start at 33°C (91.4°F). During the experiment, the computerized data acquisition system records heart rate, skin blood flow, and skin temperatures continuously. The researcher and/or an automated critical care monitor measures blood pressure at 5-7 minute intervals.

Acetylcholine, Angiotensin II, and Norepinephrine Dose Responses: The intradermal microdialysis probes are randomly numbered 1 - 4 and assigned

to receive doses of acetylcholine with or without L-NAME (probes 1 and 2), angiotensin II (probe 3) or norepinephrine (probe 4).

Acetylcholine Dose Response: Microdialysis Probe 1. Lactated Ringer's only

Microdialysis Probe 2. Lactated Ringer's + L-NAME

Angiotensin II Dose Response: Microdialysis Probe 3. Lactated Ringer's only

Norepinephrine Dose Response: Microdialysis Probe 4. Lactated Ringer's only

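### XI.1 pre-specifies no losartan test at the unblocked acetylcholine probe; a treatment main effect pooled with the L-NAME probe would understate the change in endothelium-dependent dilation, by up to half if blockade is complete.

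*Combined protocol and SAP*

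**What the plan says.** XI.1 names the outcome: "The primary outcome variable will be cutaneous vascular conductance, which is calculated from laser-Doppler flux/mean arterial pressure". It gives no probe, dose or summary measure for it. The losartan question goes to one model: "Three-way repeated measures ANOVA (treatment, MD site, dose) will be used to examine systemic treatment differences (losartan vs. placebo"; the same sentence also assigns to that model the local "microdialysis treatment differences across the doses of pharmacological stimuli". On follow-up, XI.1 says: "Appropriate post-hoc analyses with corrections for multiple comparisons will be performed when main effects are identified". Interactions are not mentioned.

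Hypothesis 1 in I.5 reads: "Chronic oral losartan therapy will augment endothelium-dependent dilation in PE by increasing nitric oxide-dependent dilation". Under VII.E.6 the four probes are assigned "to receive doses of acetylcholine with or without L-NAME (probes 1 and 2), angiotensin II (probe 3) or norepinephrine (probe 4", and the second acetylcholine site is listed as "Microdialysis Probe 2. Lactated Ringer's + L-NAME". XI.1 does not say which of the four probes form the MD site factor. VII.D.29 describes a "double-blind randomized crossover design", so each woman supplies both treatments at every probe.

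**The concern.** Hypothesis 1 has two parts: total endothelium-dependent dilation rises, and it rises through nitric oxide. Probe 1 shows the total response. Probe 2 is the mechanism control, because L-NAME is there to remove the nitric oxide component. If losartan acts mainly through nitric oxide, its effect should be present at probe 1 and small or absent at probe 2.

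The treatment main effect of the three-way ANOVA averages over sites, so it mixes the control into the losartan comparison. The closer the hypothesised mechanism is to the truth, the more the main effect is diluted. If the main effect is also what permits follow-up, a real change at probe 1 might never be tested separately. A reported pooled difference would understate the change in endothelium-dependent dilation.

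**Working it through.** **The plan's own figure.** XI.2 gives 10 subjects for a 15% effect between microdialysis sites, with alpha 0.05 and power printed as 0.08 (0.80 is presumably meant). No SD is given in the text available, and part of the background section is not in it, so the 10 cannot be reproduced. Working backwards with a paired t-test, two-sided 0.05, n = 10 and 80% power, the standardised difference is 0.996. A 15-point difference then implies an SD of differences of 15/0.996 = 15.1. The figure is attainable but unverifiable, and it concerns sites, not losartan against placebo.

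**Inputs.** From XI.2: 10 completers (20 less about 5 screen failures and about 5 dropouts) and alpha 0.05. Assumed: two-sided testing; a probe 1 losartan effect that a paired test detects with 80% power (d = 0.996); two sites in the factor; no period term, since XI.1 lists none. Varied because the documents are silent:

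- r, the correlation between the two sites' losartan-placebo differences;
- k, the SD of that difference at probe 2 relative to probe 1;
- f, the share of the losartan effect persisting at probe 2 (f = 0 is complete blockade).

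**Formulas.** In a fully within-woman ANOVA the treatment main effect is equivalent to a paired t-test on each woman's mean over sites and doses.

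- Expected pooled estimate, as a share of the probe 1 effect: (1 + f)/2. This is 0.50 at f = 0, 0.625 at f = 0.25 and 0.75 at f = 0.5.
- Main effect: d = 0.996(1 + f)/√(1 + k² + 2rk).
- Treatment x site: d = 0.996(1 − f)/√(1 + k² − 2rk).

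Power is from the noncentral t with 9 df and noncentrality d√10.

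| Case | r | Main-effect d | Main-effect power |
|---|---|---|---|
| f = 0, k = 1 | 0 | 0.996/1.414 = 0.704 | 51% |
| f = 0, k = 1 | 0.5 | 0.996/1.732 = 0.575 | 37% |
| f = 0, k = 1 | 0.8 | 0.996/1.897 = 0.525 | 32% |
| f = 0, k = 0.5 | 0 | 0.996/1.118 = 0.891 | 71% |
| f = 0, k = 0.5 | 0.5 | 0.996/1.323 = 0.753 | 57% |
| f = 0.25, k = 1 | 0 | 1.245/1.414 = 0.880 | 70% |
| f = 0.25, k = 1 | 0.5 | 1.245/1.732 = 0.719 | 53% |
| f = 0.5, k = 1 | 0 | 1.494/1.414 = 1.056 | 84% |
| f = 0.5, k = 1 | 0.5 | 1.494/1.732 = 0.863 | 68% |

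The probe 1 contrast has 80% power throughout, by construction.

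**Break-even.** With k = 1, pooling equals the probe 1 test when (1 + f)/√(2 + 2r) = 1. At r = 0 this gives f = √2 − 1 = 0.41.

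**Interaction.** Under complete blockade and equal SDs, treatment x site has 51% power at r = 0, 80% at r = 0.5 and 99% at r = 0.8. With f = 0.25 it has 32% at r = 0 and 56% at r = 0.5.

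**Gate.** In a simulation of 100,000 trials (f = 0, k = 1), requiring a significant treatment main effect and then a probe 1 test Bonferroni-corrected for two comparisons succeeded in 45% (r = 0) or 36% (r = 0.5) of trials. Letting either the main effect or the interaction open the gate gave 64% or 65%.

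**The case against.** The strongest reply is that XI.1 never designates the treatment main effect as the losartan test. It names a model that also serves the site comparison, and such a model ordinarily yields treatment x site as well. That term carries the full probe 1 effect under complete blockade, and for r of 0 or more (equal SDs) its power is never below that of the main effect. The follow-up clause does not say which main effect is meant, so a site or dose effect might open it. Hypothesis 1 does not say nitric oxide is the only route, and the documents do not say L-NAME blockade is complete.

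Most of this stands. A reader might infer that the trial tests only half the true losartan effect and loses 29 to 43 power points. The documents do not support that. Half is the limiting case, and those points arise only from the 80% anchor, 10 completers, equal SDs, complete blockade, two sites and r between 0 and 0.5. Other equally undocumented inputs give smaller losses, larger losses or a gain.

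What the reply does not remove is the gap itself. The interaction asks whether losartan's effect differs with nitric oxide availability, not whether total dilation rose. XI.1 does not name it, and the follow-up clause refers only to main effects. No stated test isolates probe 1.

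**Conclusion.** The point holds as a gap in specification with a predictable direction of harm. If losartan acts mainly through nitric oxide, the main effect over probes 1 and 2 understates the change in endothelium-dependent dilation, by up to half under complete blockade. The dilution of the estimate is algebra and needs no SD.

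The power cost depends on undocumented quantities. Against 80% at probe 1, main-effect power runs from 32% to 84% over the cases shown, and pooling gains when enough of the effect persists at probe 2 and the sites are weakly correlated. No single loss should be quoted as the trial's. The matter does not invalidate the design; it is an inexpensive improvement that should be made.

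**What to change.** Amend XI.1 as follows:

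- Test total endothelium-dependent dilation by the losartan-placebo difference at probe 1 alone, averaged over doses or as area under the dose curve, with the choice fixed in advance.
- Test nitric oxide-dependent dilation by the treatment x site contrast, probe 1 against probe 2.
- Restrict the site factor in this model to probes 1 and 2. VII.E.6 gives ten acetylcholine concentrations but nine of angiotensin II or norepinephrine, so the four probes do not share one dose factor in any case.
- Make neither test conditional on a significant main effect.
- Report the pooled main effect as descriptive.

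This changes wording only and needs no extra women, visits or measurements. The downside is a small loss of power if losartan has a substantial effect outside nitric oxide: about 41% or more of the probe 1 effect persisting at probe 2, when the sites are uncorrelated and have equal SDs.
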